A variant of FFT, FFT-Gangs, was found to be effective at engaging YP at high risk of gang involvement and was more effective in reducing recidivism at 18-month follow-up for high-risk youth (but not for low-risk youth) when compared to services as usual (SAU; Thornberry et al., 2018). We subsequently tested the feasibility of evaluating this intervention with YP at risk of CCE in UK child social care⁶. The results of this pilot RCT demonstrated that it was feasible to both implement FFT-G with this population and to evaluate it. The key results that informed the design of this efficacy study were:

1. Close alignment and shared recruitment systems between the project and evaluation team were key to successful recruitment of participants.
2. FFT-G therapists require a training period prior to randomisation starting in order to develop clinical skills and establish referral pathways. This should be a minimum of 6 months.

⁵ <https://www.blueprintsprograms.org/>

⁶ See <https://youthendowmentfund.org.uk/wp-content/uploads/2023/01/FFT-G.-YEF-Feasibility-and-Pilot.-Jan-2023.pdf>.

3. Information on risk factors is not captured and recorded reliably enough on agency systems in order to identify eligible YP (see p.65 of pilot study report). Further screening by the FFT-G supervisor/supervisor-in-training is required.
4. Between 10 and 11 eligible YP were identified per month. Randomisation rates were significantly higher when the FFT-G supervisor/supervisor-in-training screened agency systems for eligible cases rather than when they waited to receive referrals. Therefore, when screening of agency systems is conducted by the FFT-G supervisor/supervisor-in-training, we would expect 6 randomisations per site per month (see pp.56-59 of pilot study report).
5. Attrition was 20%. Missing data rates were very low but, as noted below, there were significant problems with some measures.
6. The upper end of the sample size projection (see sample size calculation section below) indicated a required sample size of 248, adjusted to 288 to account for 10% attrition at post-treatment and another 10% attrition at long-term follow-up (12 months post-randomisation). Therefore, an efficacy trial will most likely need to recruit across 3 sites over 16 months.

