Towards the end of the call, the FPM referral and data officer is invited to join the call and i) explain the study to the practitioner in more detail, ii) provide their contact details, iii) ask the practitioner to provide an information sheet to and request consent from the family for their contact details to be shared with the research team and then iv) set up a first call with the family.

[figure not shown]
Consent and assessment

The Greenwich Research Assistant (RA) meets the YP and PCG either via a Microsoft Teams video call, on the telephone or in a face-to-face meeting (in the family home or neutral venue), and explains the study to the family (PCG and YP) and obtains consent⁸. Typically, this will take place over a number of calls/meetings. If consent is given the RA will then conduct the baseline research assessment with the YP and their PCG separately. This will be in the form of an interview for the majority of cases. If the participants wish to complete the measures online on their own, then the link to a Redcap survey is provided (please also see description of primary outcome below). Translated study materials and/or interpreters will be used when required to enable informed consent and to complete the research tools.

The intervention is typically delivered in the family home or in a neutral venue if that is preferred by the family.

⁸ When it is only possible to obtain verbal consent, participants will subsequently be contacted to attempt to obtain written consent.

Figure 2: CONSORT diagram

n.b. example CONSORT diagram with anticipated numbers.

Sample size calculations

Sample size calculations are not determined on the basis of a priori MDES but rather data from the pilot RCT. [note difference from primary outcomes and direct to outcomes section for full explanation].

Sample size estimates for a full efficacy RCT were calculated using clincalc.com and checked against G*Power calculations. Estimates used 80% power and $p = 0.05$ with an enrolment ratio of 1. Power calculations used one-sided tests because there is no recorded case of FFT having iatrogenic effects.

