Two co-primary outcomes were used: PCG reported family functioning (total scale score) and YP reported conduct problems (CP; subscore of the SDQ). Based on the effect size for PCG-reported Family Functioning outcome ($g = 0.36$ (-0.32,1.03)), clincalc.com returned 238 participants, increased to 288 to account for up to 10% loss to follow-up at each assessment time point. Based on the effect size for YP-reported CP ($g = 1.15$ (0.13,1.52)), clincalc.com returned 42 participants, increased to 51 to account for 10% loss to follow-up at each assessment time point. After discussion with the YEF Assistant Director of Evaluation, the decision was taken to use the upper end of this sample size calculation range (N=288). Any harmful effects will be monitored through serious incident reporting.

Table 2: Sample size calculation

		PARAMETER
Pilot study Effect Size		$g = 0.36$ [-0.32,1.03]
Pre-test/ post-test correlations	level 1 (participant)	0.523
Alpha ⁹		0.05
Power		0.8

⁹ Please adjust as necessary for trials with multiple primary outcomes, 3-arm trials, etc., when a Bonferroni correction is used to account for family-wise errors.

		PARAMETER
One-sided or two-sided?		One sided
Number of participants	Intervention	144
	Control	144
	Total	288

Outcome measures

Details on primary and secondary outcomes and other variables are provided below. Table 3 provides contextual information on the outcomes relating to offending and CCE.

Outcome data collection points

There are three data collection points: at baseline prior to randomisation; post-treatment: six months after randomisation; follow-up: twelve months after randomisation.

Unless specified below, all measures will be collected by a University of Greenwich researcher at all time points.

Table 3: Outcome terminology

Terminology	
Offending behaviours	Offending behaviours refer to behaviours that break the law. The YEF refer to three types of offending behaviours: (a) non-violent crime (viz. that do not involve violence against another person such as shoplifting, graffiti, using illegal drugs); (b) sexually violent crime; and (c) violent crime against another person (e.g., assault, robbery using threat or force, homicide)

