		Attachment representation measured by YP report: AAQ (Bodfield et al., 2020)	

YP self-efficacy measured by YP report: NGSE (Chen et al., 2001)

CU traits measured by YP and parent report: CU Traits MAP (Hawes et al., 2020)

Temperamental irritability measured by YP report: ODD subtyping DSM items (Stringaris & Goodman, 2009)

YP School attendance and truancy measured by parent report; and YP report from ISRD4

Age; gender; ethnicity; SES; household composition; parent relationship to YP measured by parent and/or YP report

Service being seen; days from first caseworker contact to randomisation measured by administrative data

Sample size calculations overview

Sample size calculations are not determined on the basis of a priori MDES but rather results from the pilot RCT.

		Protocol	Randomisation
Pilot study Effect Size		g = 0.36 [-0.32,1.03]	
Pre-test/ post- test correlations	level 1 (participant)	0.523	
Alpha ⁶		0.05	
Power		0.8	
One-sided or two-sided?		One sided	

⁶ Please adjust as necessary for trials with multiple primary outcomes, 3-arm trials, etc., when a Bonferroni correction is used to account for family-wise errors.

9

			Protocol	Randomisation
Number of participants		Intervention	144	
	of	Control	144	
	Total	288		

Sample size estimates for a full efficacy RCT were calculated using clincalc.com and checked against G^* Power calculations. Estimates used 80% power and p = 0.05 with an enrolment ratio of 1. Power calculations used one-sided tests because there is no recorded case of FFT having iatrogenic effects.

The primary outcome in the efficacy study is *Offending*: Self-reported delinquency (SRD) - International Self-Report Delinquency Study 4 survey offending scale (ISRD4; Marshall et al., 2022). This was not the primary outcome in the pilot study. Whilst a number of trials of FFT have been conducted with offending as a primary outcome, and a previous trial of FFT-G did include delinquency as a primary outcome, it recruited court mandated youth who were offending. The focus of the pilot was instead YP at risk of criminal exploitation recruited from social care.

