Therefore, the anticipated primary outcome in the pilot study was CCE as recorded on agency systems. During the pilot study, it became clear that this was not recorded reliably and so two co-primary outcomes collected directly from participants were used instead: PCG reported family functioning (total scale score) and YP reported conduct problems (CP; subscore of the SDQ). As a result, power calculations for this efficacy trial did not make use of SRD data from the pilot study. Based on the effect size for PCG-reported Family Functioning outcome in the pilot study (g = 0.36 (-0.32,1.03)), clincalc.com returned 238 participants, increased to 288 to account for up to 10% loss to follow-up at each assessment time point. Based on the effect size for YP-reported CP (g = 1.15 (0.13,1.52)), clincalc.com returned 42 participants, increased to 51 to account for 10% loss to follow-up at each assessment time point. After discussion with the YEF Assistant Director of Evaluation, the decision was taken to use the upper end of this sample size calculation range (N=288). Any harmful effects will be monitored through serious incident reporting. The pre-test/post-test correlation also mirrors the results of the pilot trial (i.e., 0.523).

However, as subsequently requested by the YEF, this trial will use self-reported delinquency as the primary outcome. The rationale for this is:

- A core YEF strategic aim is to understand what works to reduce crime and violence, so YEF aims to select offending as the primary outcome in all YEF studies where it is plausible that the intervention will reduce it, e.g. it is included in the theory of change
- The primary outcome must be measured using a valid and reliable measure and there were no valid and reliable measures of other relevant outcomes that are highly connected to crime e.g. child criminal exploitation.
- The mitigations included since the pilot study to increase the chance of seeing impact on offending (e.g. screening YP, introducing anonymous reporting of outcomes by YP)
- The co-primary outcomes from the pilot study will be included as secondary outcomes so that it will still be possible to test for intervention effects on these.

Participants

Participants will be YP between 10-17 at risk of CLDN involvement or CCE being seen by child social care or related agencies in three London local authorities and their primary caregiver (PCG).

Inclusion criteria - YP and families

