imputation techniques but the precise techniques used will depend on the pattern and extent of missingness. We will comply with the YEF Guidance on Missing Data.

Compliance

We use FFT LLC's own guidance of defining and measuring family compliance with the intervention. This stipulates that the total dose will depend on the needs of the family. However, we will report on the number of families who attended at least one session, and consider how many families moved through how many phases of treatment, how many received a critical dose of 8 sessions, mean number of sessions received and how many were deemed to have completed treatment. We will also report on therapist fidelity to the FFT model. This data will be provided by FFT LLC using the clinical monitoring system completed by FPM therapists. We will also explore whether time from referral to first FFT session is associated with compliance and improvement in outcomes. If power permits, we will explore whether compliance and fidelity are associated with improvements in the primary outcome and in CCE and SDQ conduct problems.

As advised by the YEF Statistical Guidance we will use an Instrumental Variable approach. This will use a Two Stage Least Square Analysis guidance (2SLS) approach with group allocation as the instrumental variable for the compliance indicator. Results for the first stage will be reported alongside with i) the correlation between the instrument and the endogenous variable; and, ii) a F test.

Intra-cluster correlations (ICCs)

This is not applicable to the current trial.

Presentation of outcomes

Effect sizes will be calculated using Hedges' g. Hedges' g is specified using the following formula:

```
Hedges' g = (x1 - x2) / V((n1-1)*s12 + (n2-1)*s22) / (n1+n2-2) where:
```

x1, x2: The sample 1 mean and sample 2 mean, respectively

n1, n2: The sample 1 size and sample 2 size, respectively

s12, s22: The sample 1 variance and sample 2 variance, respectively

The confidence interval for the Hedge's g statistic is:

g±φ - 1 (1-(α /2))gse where:

 ϕ - 1 = the percent point function of the normal distribution

gse= the standard error of the g statistic

 $= \sqrt{(n1+n2)/n1n2 + g^2/2(n1+n2)}$

References

We will add in to revised version.

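### The stated sample-size inputs (g = 0.36, one-sided 5%, 80% power) give 192 participants, not 238 or 248, and neither document fixes the side or level of the primary test

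*Protocol*

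**What the plan says.** The Protocol (Sample size calculations, Table 2) and the SAP (Sample size calculations overview) list the same parameters: pilot effect size g = 0.36, pre/post correlation 0.523, alpha 0.05, power 0.8, one-sided. The SAP text adds: "Estimates used 80% power and p = 0.05 with an enrolment ratio of 1". Both documents give the reason for the side: "Power calculations used one-sided tests because there is no recorded case of FFT having iatrogenic effects".

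For caregiver-reported family functioning, the Protocol says "clincalc.com returned 238 participants, increased to 288 to account for up to 10% loss to follow-up at each assessment time point". The SAP gives the same base: "g = 0.36 (-0.32,1.03)), clincalc.com returned 238 participants". Item 6 of the pilot results in the Protocol's Study rationale and background gives another: the projection "indicated a required sample size of 248, adjusted to 288 to account for 10% attrition at post-treatment", with a further 10% at 12 months.

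For the second pilot outcome, young-person-reported conduct problems, both documents report that g = 1.15 required 42 participants, raised to 51.

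The analysis sections (Protocol, Analysis; SAP, Analysis and Primary outcome analysis) specify a linear mixed model with the main test at 12 months. They give no side and no significance level. In the SAP's Presentation of outcomes, the interval for Hedges' g takes its multiplier, "the percent point function of the normal distribution", at 1 − α/2, which is the two-sided form.

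**The concern.** A one-sided 5% test needs fewer participants than a two-sided one, and 238 looks too large for the one-sided label at g = 0.36. If the label and the number do not belong together, the stated power is wrong for the stated test, and the reader cannot tell which test the trial was sized for.

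This matters beyond the arithmetic. The one-sided label is the only explicit statement of sidedness in either document, and the interval formula points the other way. With no decision rule in the analysis sections, the choice between z > 1.645 and z > 1.96 stays open until the data are analysed.

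**Working it through.** **Inputs.** g = 0.36, alpha 0.05, power 0.80, 1:1 allocation and r = 0.523, all from the two sample-size sections. Loss of 10% at each of two follow-ups is from the same text.

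**Formula.** n per arm = 2(z_α + z_β)² / g², with z_β = 0.8416; z_α = 1.6449 one-sided or 1.9600 two-sided.

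**Attempt to reproduce 238.**
- One-sided: 2(1.6449 + 0.8416)² / 0.1296 = 95.4, so 96 per arm, N = 192 (194 by an exact t calculation).
- Two-sided: 2(1.9600 + 0.8416)² / 0.1296 = 121.1, so 122 per arm, N = 244 (246 by t).

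| Variant | One-sided N | Two-sided N |
|---|---|---|
| g = 0.36 | 192 | 244 |
| g from 0.355 to 0.365 (rounding) | 198 to 186 | 250 to 236 |
| Change score, factor 2(1 − 0.523) = 0.954 | 184 | 232 |
| Baseline-adjusted, factor 1 − 0.523² = 0.726 | 140 | 176 |

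No one-sided entry reaches 238 or 248. Both figures lie inside the two-sided rounding range.

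**A second route to 238.** One-sided 96 per arm, inflated for two 10% losses: 96 / (0.9 × 0.9) = 118.5, so 119 per arm, N = 238.

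**Attrition step.** 238 × 1.1 × 1.1 = 287.98, which gives the stated 288. Dividing by the retained fraction would give 238 / 0.81 = 293.8, so 294. From 248 the results are 300 (× 1.21) or 307 (/ 0.81), so 248 does not lead to 288.

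**Power for g = 0.36**, as Φ(g√(n/2) − z_α) with n per arm:
- 238 analysed (n = 119): g√(n/2) = 2.777. One-sided Φ(1.132) = 87.1%; two-sided Φ(0.817) = 79.3%.
- 288 × 0.81 = 233.3 completers (n = 116.6): g√(n/2) = 2.749. One-sided 86.5%; two-sided 78.5%.

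**Second outcome.** g = 1.15 gives 20 one-sided or 24 two-sided (22 or 26 by t), not 42. The step from 42 to 51 is again × 1.21 (50.8).

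**Where test and interval would part.** With a one-sided 5% test and a 95% two-sided interval, any z between 1.645 and 1.960 passes the test while the interval includes zero. At g = 0.36 with 238 analysed the chance of this is 87.1% − 79.3% = 7.8%; under no effect it is 5% − 2.5% = 2.5%.

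**The case against.** A reader might infer that 238 and 248 can only be two-sided results. The documents do not support that. At the printed g a two-sided calculation gives 244; 238 needs g of about 0.363 and 248 needs about 0.356. The one-sided route through 96 / 0.81 reaches 238 with g unchanged. It conflicts with the text, which treats 238 as the base that was then "increased to 288 to account for up to 10% loss to follow-up at each assessment time point", so on that route attrition was counted twice. The means and SDs entered in the calculator are not given, and 42 fits neither side, so the origin of 238 cannot be settled. Failure to reproduce is all that is established.

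A reader might also infer that the primary test is one-sided, with a looser threshold than the one behind 238 and a false-positive rate for benefit of 5% in place of 2.5%. No section says so. The one-sided label describes the power calculation only, and the SAP's interval is two-sided. That consequence is conditional on how the test is run.

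Two further points stand. The numerical error is on the safe side: under the one-sided label power is understated, and under a two-sided test it is within about two points of 80%. And these power figures describe pilot caregiver-reported family functioning. Both documents say openly that self-reported delinquency data were not used for power, so neither the 87% and 79% nor the 7.8% describes the ISRD4 test. The SAP's interval is also for an unadjusted Hedges' g, which could disagree with the mixed-model test whatever its side.

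**Conclusion.** The concern holds as a failure to reproduce plus an unstated decision rule. The printed inputs give 192 (186 to 198), so 238 is about 24% too large for its label, and 248 is inconsistent both with 238 and with 288. Power for g = 0.36 is about 87% one-sided or 79% two-sided with 238 analysed, and 86.5% or 78.5% with about 233 completers.

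These figures assume an unadjusted two-group comparison with the normal approximation and exactly 10% loss at each follow-up. Adjusting for baseline at r = 0.523 would raise power at 238 to about 95% one-sided or 90% two-sided, so it does not restore 80% either.

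The side and level of the 12-month test are missing from both documents, and the two available hints conflict. That needs settling before analysis. Whether the eventual threshold is loose cannot be judged from the documents.

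**What to change.** 1. In both sample-size tables and texts, give one base number with the side and power that reproduce it. At 238 analysed and g = 0.36 this is either two-sided 5% with about 79% power, or one-sided 5% with about 87%. Changing the label to two-sided while leaving power at 0.8 would not be enough, because that needs 244, which inflates to 296 (× 1.21) or 302 (/ 0.81).
2. State beside it that the calculation concerns pilot family functioning and that power for the ISRD4 primary outcome has not been established.
3. Reconcile 248 in the Protocol's background section with 238, state how attrition was applied, and correct or remove the 1.15 / 42 / 51 figures.
4. In the SAP's Primary outcome analysis, state one side and alpha for the 12-month test and report a matching interval. Two-sided 5% fits the interval formula already in the SAP. If one-sided is kept, report a matching one-sided bound.

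The cost is wording in two tables and a few sentences. N = 288 need not change once the power is restated. The Protocol's timeline already schedules a SAP update for November 2025, before data cleaning and analysis begin in July 2026.

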Appendix 1: Changes since the previous YEF evaluation¹⁵

Appendix Table 1: Changes since the previous evaluation¹⁶

Feature		Pilot to efficacy stage
Intervention	Intervention content	Addition of floating FFT-G therapist
	Delivery model	None
	Intervention duration	None
Evaluation	Eligibility criteria	None
	Level of randomisation	None but stratification by site introduced
	Outcomes and baseline	Primary outcome changed to ISRD offending scale. Some secondary outcomes changed.

¹⁵ Please delete this section if it is not applicable.

¹⁶ Delete columns from the table if they are not applicable or adjust titles as relevant.

	Control condition	No changes.
--	--------------------------	-------------

Appendix 2

Functional Family Therapy - Gangs

Statistical analysis plan

Evaluating institution: University of Greenwich

Principal investigator(s): [name], [name],

[name]

YEF statistical analysis plan

Project title¹	Efficacy Randomised Trial of Functional Family Therapy – Gangs	
Developer (Institution)	FFT-LLC	
Evaluator (Institution)	University of Greenwich	
Principal investigator(s)	[name], [name], and [name]	
Protocol author(s)	[name], [name], and [name]	
Trial design	Two-armed randomised parallel multi-site efficacy trial with randomisation at the level of the Young Person	
Trial type	Efficacy RCT	
Evaluation setting Family, child social care and associated agencies in three Authorities in London		
Target group	10- to 17-year-olds at risk of criminal exploitation	

_

¹ Please make sure the title matches that in the header and that it is identified as a randomised trial as per the CONSORT requirements (CONSORT 1a).

Number of participants	288	
Primary outcome and data source	Offending: Self-reported delinquency - International Self-Report Delinquency Study 4 survey offending scale (ISRD4; Marshall et al., 2022).	
	Young People's (YP) mental health and adjustment measured by Parent and YP report: Strengths and Difficulties Questionnaire (Goodman, 2001)	
	Child Criminal Exploitation measured by YP report: International Self-Report Delinquency (ISRD) 4 additional items.	
	Substance Misuse measured by YP report: ISRD3 substance misuse subscale ² .	
Secondary outcome and data source	Parental mental health measured by parent report: Depression, Anxiety and Stress Scale (DASS-21; Henry & Crawford, 2005)	
	Parenting supervision, knowledge and YP disclosure measured by YP report (ISRD4).	
	Family Functioning measured by YP and parent report: SCORE-15 Index of Family Functioning and Change (Fay et al., 2013)	
	Parental self-efficacy measured by parent report: Brief Parental Self-Efficacy Scale (BPSES; Woolgar et al., 2023)	
	Attachment representation measured by YP report: Adult Attachment Questionnaire (AAQ; Bodfield et al., 2020)	

 $^{^2\ {\}it http://www.northeastern.edu/isrd/general-isrd-3-publications/}$

YP self-efficacy measured by YP report: New General Self-Efficacy Scale (NGSE; Chen et al., 2001)

Callous-Unemotional traits measured by YP and parent report: Callous-Unemotional Traits Maximum A Posteriori Scale; (CU Traits MAP; Hawes et al., 2020)

Temperamental irritability measured by YP report: Oppositional Defiant Disorder (ODD) subtyping Diagnostic and Statistical Manual (DSM) items (Stringaris & Goodman, 2009)

YP School attendance and truancy measured by parent report; and YP report from ISRD4: E2/3

Age; sex; gender; ethnicity; Socio-Economic Status (SES); household composition; parent relationship to YP measured by parent and/or YP report

Service being seen; days from first caseworker contact to randomisation measured by administrative data

SAP version history

Version	Date	Changes made and reason for revision
1.2	07.08.2024	Revised following additional YEF comments
1.1	14.06.2024	Revised following YEF comments and peer review
1.0 [original]	15.04.24	

Table of contents

Contents

SAP version history	3
Table of contents	4
ntroduction	5
Design overview	6
Sample size calculations overview	9
Analysis	.12
References	. 18

Introduction

County Lines Drug Networks (CLDNs) are organised networks involving the transportation of primarily class A drugs from urban to rural areas (Home Office, 2022). CLDNs were originally conceptualised as the activity of criminal gangs (National Crime Agency [NCA], 2016) but are now understood to also be an activity of organised crime groups³ (OCGs; Home Office, 2022). Gangs and OCGs establish a network between an urban hub and rural areas where drugs are sold using a branded mobile telephone line through which orders are placed. Vulnerable children (under 12), young people (YP) and adults are exploited in order to transport, store and distribute drugs (ibid.). They are also likely to be encouraged or coerced into engaging in a range of other criminal activities, including violence against other YP. CLDNs are subsumed under the broader definition of child criminal exploitation (CCE), as defined by the Home Office (2022).

YP who are being criminally exploited are typically vulnerable and are at high risk for violent victimisation and Child Sexual Exploitation (CSE). CLDN violent crime can involve kidnapping and robbery, scalding victims with the use of boiling water or corrosive materials and sexual violence, with the latter being used more commonly against girls (Coliandris, 2015; NCA, 2017; Robinson et al., 2019; Williams and Finlay, 2019). Various factors (including poverty, ethnic minority background, family breakdown, in the care of social services, being missing from home and school exclusion) all appear to increase the risk of child criminal exploitation. Furthermore, the YEF's Children, Violence and Vulnerability (CVV) report⁴ noted that overrepresentation of Black children in the youth justice system was increasing and that children from ethnic minority backgrounds were not being given access to the early support from services that they needed.

Functional Family Therapy (FFT; Alexander et al., 2013) is a promising evidence-based intervention that possesses evidence of delivering positive outcomes and engaging and retaining hard-to-reach YP and their families (Hartnett, Carr and Sexton, 2016), a clear challenge when working with those who are gang-involved or at risk of CCE. Contextual factors such as economic disadvantage, structural racism and inequity, play a key part in tackling the root causes of youth crime and violence.

We tested the feasibility of evaluating FFT-Gangs (FFT-G), an adaptation of FFT designed to reduce gang affiliation and related criminal behaviour, with YP at risk of CCE in UK child social

 $^{^3 \} See \ https://www.local.gov.uk/sites/default/files/documents/tackling-serious-and-orga-44a.pdf$

⁴ https://youthendowmentfund.org.uk/reports/children-violence-and-vulnerability-2022/

care⁵. The results of this pilot RCT demonstrated that it was feasible to both implement FFT-G with this population and to evaluate it. This efficacy study builds on the learning from this pilot trial and aims to assess the effect of FFT-G on levels of self-reported delinquency in YP at risk of CCE, CLDN involvement and other extra-familial harm.

Design overview

This is a parallel, two-armed, multi-site, efficacy randomised controlled trial of FFT-G compared to Services as Usual (SAU) interventions, in child social work, youth offending and early intervention services for YP at risk of Child Criminal Exploitation (CCE). This will use block randomisation with randomly varying block sizes of 4 or 6 with equal allocation ratio in order to ensure the research team are blind to the randomisation outcome. We will use small block sizes to ensure full caseloads for the clinical teams. The YP will be the unit of randomisation with an allocation ratio of 1:1, stratified by recruiting site. All study participants will have an allocated caseworker and will receive statutory or other services provided or organized by child social care and other agencies (e.g., early help, Youth Offending Services). In addition, the intervention arm will receive FFT-G and the SAU arm will receive additional specialist services identified prior to randomisation.

Trial design, including number of arms		Two-arm randomised, stratified, parallel group, multi-site efficacy trial
Unit of randomisation		Young person
Stratification variables (if applicable)		Site
Drimon	variable	Offending
Primary outcome	measure (instrument, scale, source)	Measured by YP report: International Self-Report Delinquency Study 4 survey offending scale (ISRD4; Marshall et al., 2022)

_

⁵ See https://youthendowmentfund.org.uk/wp-content/uploads/2023/01/FFT-G.-YEF-Feasibility-and-Pilot.-Jan-2023.pdf.

	variable(s)	YP mental health and adjustment; Child Criminal Exploitation; substance misuse; parental mental health; parental monitoring and supervision; family functioning; parental self-efficacy; attachment representation; YP self-efficacy; Callous-Unemotional (CU) traits; temperamental irritability; school attendance and truancy; age; gender; ethnicity; SES; household composition; service being seen; parent relationship to YP; days from first caseworker contact to randomisation.
	measure(s) (instrument, scale, source)	YP mental health and adjustment measured by Parent and YP report: Strengths and Difficulties Questionnaire (Goodman, 2005)
		Child Criminal Exploitation measured by YP report: SRD4 additional items.
		Substance Misuse measured by YP report: ISRD3 substance misuse subscale (Marshall et al., 2013).
Secondary		Parental mental health measured by parent report: DASS-21 (Henry & Crawford, 2005)
outcome(s)		Parenting supervision, knowledge and YP disclosure measured by YP report: ISRD3 (Marshall et al., 2013).
		Family Functioning measured by YP and parent report: SCORE-15 (Fay et al., 2013)
		Parental self-efficacy measured by parent report: BPSES (Woolgar et al., 2023)
